8. SELECTION AND WITHDRAWAL OF SUBJECTS

8.1. Subject Inclusion Criteria

1. Male or female ≥ 18 years age at the time of consent.
2. Eastern Cooperative Oncology Group (ECOG) performance status 0 to 2.
3. Has the ability to understand informed consent and provide signed written informed consent.
4. Life expectancy of > 3 months.
5. Histologically and/or cytologically confirmed advanced metastatic or unresectable solid tumors has progressed after treatment for which there are no standard therapies available OR histologically and/or cytologically confirmed hematologic malignancies that have relapsed, or refractory disease, following at least 2 standard lines of systemic therapy for which there are no standard therapies available.
Note: Subjects with prior radiotherapy will be included; however, radiotherapy alone will not be considered a separate systemic treatment regimen.
6. Must have evaluable or measurable disease.
7. Has all prior treatment (ie, chemotherapy, immunotherapy, radiotherapy) related clinically significant toxicities resolve to \leq Grade 1 per National Cancer Institute Common Terminology Criteria for Adverse Events (NCI CTCAE), Version 5.0 or are clinically stable and not clinically significant, at time of consent.
8. All subjects must have completed any prior chemotherapy, targeted therapy and major surgery ≥ 28 days before study entry. For daily or weekly chemotherapy without the potential for delayed toxicity, a washout period of 14 days or 5 half-lives, whichever is shorter may be acceptable, and questions related to this can be discussed with the Medical Monitor.
9. Has normal hepatic function as well as adequate hematologic (bone marrow [BM] and coagulation factors) and renal function (Table 5).

Table 5: Laboratory Values for Hepatic, Hematologic and Renal Function

System	Laboratory Value
Hematologic (BM Function)	
Hemoglobin ^a	≥ 9 g/dL (90 g/L)
Platelets ^b	$\geq 75,000/\text{mm}^3$ ($\geq 75 \times 10^9/\text{L}$)
ANC ^c	Hematologic malignancy subjects: $\geq 1,000/\text{mm}^3$ ($\geq 1.0 \times 10^9/\text{L}$) Solid tumor subjects: $\geq 1,500/\text{mm}^3$ ($\geq 1.5 \times 10^9/\text{L}$)
Hematologic (Coagulation Factors)	
PT/INR	< 1.5 ULN
aPTT	< 1.5 ULN
Renal Function	
Serum creatinine ^d	$\leq 1.5 \times$ ULN

System	Laboratory Value
Normal Hepatic Function (per NCI-ODWG criteria)	
Total bilirubin, AST, and ALT	≤ ULN

Abbreviations: ANC = absolute neutrophil count; AST = aspartate aminotransferase; ALT = alanine aminotransferase; BM = bone marrow; eGFR = estimated glomerular filtration rate; INR = international normalized ratio; PT = prothrombin time; aPTT = activated partial thromboplastin time; ULN = upper limit of normal

^a May receive transfusion.

^b Should be evaluated after at least 7 days since last platelet transfusion.

^c Without growth factor support (filgrastim or pegfilgrastim) for at least 14 days.

^d If serum creatinine is not $\leq 1.5 \times$ ULN, then calculate eGFR by Chronic Kidney Disease Epidemiology Collaboration (CKD-EPI) Creatinine Equation (2009) ([Appendix 3](#)). eGFR must be ≥ 50 mL/min/1.73 m².

Note: Laboratory results obtained during screening should be used to determine eligibility criteria. In situations where laboratory results are outside the permitted range, the Investigator may retest the subject and the subsequent within range screening result may be used to determine the subject's eligibility. Subjects may be retested once within 2 weeks of the screening test. Samples must be reanalyzed at the local laboratory.

10. Able to swallow and retain orally-administered medication and without clinically significant gastrointestinal abnormalities that could alter absorption such as malabsorption syndrome or major resection of the stomach or bowels.
11. Manual differential with no significant morphologic abnormalities other than those associated with the subject's diagnosed type of advanced malignancy on complete blood count (CBC) testing.
12. Females of childbearing potential (FCBP) must have a negative serum pregnancy test (beta-human chorionic gonadotropin [β -hCG] test with a minimum sensitivity of 25 mIU/mL or equivalent units of β -hCG) at screening and within 24 hours prior to the first dose of study drug. All females will be considered to be of childbearing potential unless they are naturally postmenopausal (at least 12 months consecutively amenorrhoeic [amenorrhea following cancer therapy does not rule out childbearing potential] and without other known or suspected cause) or have been sterilized surgically (ie, total hysterectomy and/or bilateral oophorectomy, with surgery completed at least 28 days prior to the first dose of study drug).
13. Females of childbearing potential (FCBP) must either practice complete abstinence or agree to use a highly effective method of contraception beginning at least 28 days prior to the first dose of study drug, during study treatment (including during dose interruptions), and for 6 months after study drug discontinuation. If the below contraception methods are not appropriate for the FCBP, she must be referred to a qualified contraception provider to determine the medically effective contraception method appropriate for the subject. The following are examples of highly effective methods of contraception (result in a failure rate of <1% per year when used consistently and correctly):
 - Intrauterine device (IUD)
 - Intrauterine hormone-releasing system (IUS)

- Hormonal (ovulation inhibitory combined [estrogen and progesterone]: oral, intravaginal, or transdermal; ovulation inhibitory progesterone-only: oral, injectable, or implantable)

NOTE: Due to the potential of enzyme induction with tazemetostat, hormonal contraception methods must be supplemented with a barrier method of contraception (preferably male condom)

- Bilateral tubal ligation
- Partner's vasectomy (if medically confirmed [azoospermia] and sole sexual partner)

NOTE: Female subjects of childbearing potential exempt from these contraception requirements are subjects who practice complete abstinence from heterosexual sexual contact. True abstinence is acceptable when this is in line with the preferred and usual lifestyle of the subject. Periodic abstinence (eg, calendar, ovulation, symptothermal, or post-ovulation methods) and withdrawal are not acceptable methods of contraception.

14. Male subjects must have had a successful vasectomy (with medically confirmed azoospermia) OR must either practice complete abstinence or agree to use a latex or synthetic condom during sexual contact with a female of childbearing potential (FCBP) from the first dose of study drug, during study treatment (including during dose interruptions), and for 3 months after study drug discontinuation.

NOTE: Male subjects must not donate sperm from the first dose of study drug, during study treatment (including during dose interruptions), and for 3 months after study drug discontinuation.

15. Has a QT interval corrected by Fridericia's formula (QTcF) ≤ 450 msec.
16. Subjects with diagnosed human immunodeficiency virus (HIV) are eligible to participate in the study if they meet the following criteria:
- a. No history of AIDS-defining opportunistic infections or have not had an opportunistic infection within the past 12 months prior to enrollment.
 - b. No history of AIDS-defining cancers (eg, Kaposi's sarcoma, aggressive B-cell lymphoma, and invasive cervical cancer).
 - c. Subjects may take prophylactic antimicrobials, however subjects that are taking specific antimicrobial drugs where there may be drug-drug interaction or overlapping toxicities should be excluded from study participation (Table 7 and Table 8).
 - d. Subjects should be on established anti-retroviral therapy for at least 4 weeks and have an HIV viral load of < 400 copies/mL prior to enrollment.

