^c Without growth factor support (filgrastim or pegfilgrastim) for at least 14 days.

^d If serum creatinine is not $\leq 1.5 \times$ ULN, then calculate eGFR by Chronic Kidney Disease Epidemiology Collaboration (CKD-EPI) Creatinine Equation (2009) ([Appendix 3](#)). eGFR must be ≥ 50 mL/min/1.73 m².

Note: Laboratory results obtained during screening should be used to determine eligibility criteria. In situations where laboratory results are outside the permitted range, the Investigator may retest the subject and the subsequent within range screening result may be used to determine the subject's eligibility. Subjects may be retested once within 2 weeks of the screening test. Samples must be reanalyzed at the local laboratory.

10. Able to swallow and retain orally-administered medication and without clinically significant gastrointestinal abnormalities that could alter absorption such as malabsorption syndrome or major resection of the stomach or bowels.
11. Manual differential with no significant morphologic abnormalities other than those associated with the subject's diagnosed type of advanced malignancy on complete blood count (CBC) testing.
12. Females of childbearing potential (FCBP) must have a negative serum pregnancy test (beta-human chorionic gonadotropin [β -hCG] test with a minimum sensitivity of 25 mIU/mL or equivalent units of β -hCG) at screening and within 24 hours prior to the first dose of study drug. All females will be considered to be of childbearing potential unless they are naturally postmenopausal (at least 12 months consecutively amenorrhoeic [amenorrhea following cancer therapy does not rule out childbearing potential] and without other known or suspected cause) or have been sterilized surgically (ie, total hysterectomy and/or bilateral oophorectomy, with surgery completed at least 28 days prior to the first dose of study drug).

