A screening visit will occur within 30 days of signing an informed consent form (ICF). During the screening phase, subjects will be evaluated for eligibility to participate in the study. Subjects who meet the protocol criteria may be admitted in the evening to the clinical study center, or visit the clinic if staying locally, on day -1. For Cycle 1, subjects may be admitted to the clinical study center during PK sampling periods or must agree to stay locally with frequent clinic visits as required and, optional admission to the center, if available. Prior to dosing on day 1 of Cycle 1, subject eligibility will be reconfirmed. On day 1, a single oral dose of 400 mg tazemetostat will be administered in the morning (eg, 7 – 9 am) followed by 2 days of multiple blood sampling (day 1 – 3). From day 3 – 14, subjects will receive an oral 400 mg dose of tazemetostat twice daily (12 hours apart, once in the morning [eg, 7 – 9 am] and once in the evening [eg, 7 – 9 pm]). In the evening of day 14, subjects may be admitted to the clinical study center. On day 15, a single oral dose of 400 mg tazemetostat will be administered in the morning (eg, 7 – 9 am) followed by 3 days of multiple blood sampling (day 15 – 18). From day 18 – 20, a single dose of oral 200 mg itraconazole will be administered daily in the morning (eg, 7 – 9 am) after a meal. In the evening of day 20, subjects may be admitted to the clinical study unit. From day 21 – 35, subjects will receive an oral 400 mg dose of tazemetostat twice daily, once in the morning (eg, 7 – 9 am) and once in the evening (eg, 7 – 9 pm), co-administered in the morning (eg, 7 – 9 am) after a meal with a single dose of oral 200 mg itraconazole followed by 1 day of multiple blood sampling (day 21 – 22). In the evening of day 35, subjects may be admitted to the clinical study center. On day 36, subjects will receive a single oral dose of 400 mg tazemetostat co-administered in the morning (eg, 7 – 9 am) after a meal with a single dose of oral 200 mg itraconazole followed by 3 days of multiple blood sampling (day 36 – 39). Itraconazole will also be administered on day 37 and 38 as a single oral 200 mg daily dose in the morning (eg, 7 – 9 am) after a meal. **Note:** Tazemetostat will not be administered on day 37 and 38. After the 72-hour PK sample collection, safety assessments will be conducted on day 39. Sparse PK samples will be collected pre-dose (0 hour) and 2 hours post-dose on day 25, 28, 31, and 34.

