- ^d For Cycle 1 subjects may be admitted to the clinical study center during PK sampling periods or must agree to stay locally with frequent clinic visits as required and optional admission to the center if available. Subjects may have the option to be admitted to the clinical study center in the evening of day -1, 14, 20, and 35. During these admissions, laboratory assessments may be performed within 24 hours prior to when required on day 1, 15, 21, and 36.
- ^e **Clinic Visit:** Subjects will visit the clinical study unit from day -1 to day 3, from day 15 to 18, 21 to 22, 25, 28, 31, 34, and from day 36 to day 39 (Cycle 1). Cycle 2 day 1 will begin on day 40 (+ 3 days) and for subsequent cycles, clinic visit will be on day 1 (± 3 days). There will be a final clinic visit at the end of study.
- ^f **Medical History/Current Medical Conditions:** General and disease-specific medical history including a history of past and current medical conditions will be recorded during screening. Current medical conditions will be updated on day -1.
- ^g **Demographics:** Date of birth, gender, ethnicity, and race must be recorded.
- ^h **Prior and Concomitant Medications:** All prior medications administered 30 days before study drug administration will be recorded. Concomitant medications will be recorded throughout the study.
- ⁱ **Pregnancy/Post-Menopausal Testing:** For all FCBP, a serum pregnancy test must be performed at screening and within 24 hours (day -1) of the first dose of study drug in Cycle 1. For Cycle 2+, pregnancy testing to be performed on day 1 of each cycle prior to dosing of study drug. Subsequent testing at Cycle 2+ and at the end of study visit can be either urine or serum. Any positive urine pregnancy test must be confirmed with a serum test. Postmenopausal females: defined as 12 months with no menses prior to screening and a serum follicle-stimulating hormone (FSH) >40 IU/L at screening only.

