^b **End of Study:** Subjects will have a safety follow-up visit, including disease assessment, 30 (\pm 3) days after the last dose of tazemetostat, or prior to initiation of an investigational agent or cytotoxic chemotherapy, whichever occurs first. A blood sample will also be required for PK assessment.

^c Prior to dosing, assessments must be performed to determine if subject continues to meet eligibility criteria. If screening assessments are preformed within 24 hours prior to day -1 (baseline assessments), ie, day -2, they do not need to be repeated on day -1.

^d For Cycle 1 subjects may be admitted to the clinical study center during PK sampling periods or must agree to stay locally with frequent clinic visits as required and optional admission to the center if available. Subjects may have the option to be admitted to the clinical study center in the evening of day -1, 14, and 23. During these admissions, laboratory assessments may be performed within 24 hours prior to when required on day 1, 15 and 24.

^e **Clinic Visit:** Subjects will visit the clinical study unit from day -1 to day 3, from day 15 to 17, 19, 21, and from day 24 to day 26 (Cycle 1). Cycle 2 day 1 will begin on day 27 (+ 3 days) and for subsequent cycles, clinical visit will be on day 1 (\pm 3 days). There will be a final clinic visit at the end of study.

^f **Medical History/Current Medical Conditions:** General and disease-specific medical history including a history of past and current medical conditions will be recorded during screening. Current medical conditions will be updated on day -1.

^g **Demographics:** Date of birth, gender, ethnicity, and race must be recorded.

^h **Prior and Concomitant Medications:** All prior medications administered 30 days before study drug will be recorded. Concomitant medications will be recorded throughout the study.

ⁱ **Pregnancy/Post-Menopausal Testing:** For all FCBP, a serum pregnancy test must be performed at screening and within 24 hours (day -1) of the first dose of study drug in Cycle 1. For Cycle 2+, pregnancy testing to be performed on day 1 of each cycle prior to dosing of study drug. Subsequent testing at Cycle 2+ and at the end of study visit can be either urine or serum. Any positive urine pregnancy test must be confirmed with a serum test. Postmenopausal females: defined as 12 months with no menses prior to screening and a serum follicle-stimulating hormone (FSH) >40 IU/L at screening only.

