12.3.10. Pregnancy/Post-Menopausal Testing

For all FCBP, a serum pregnancy test must be performed at screening and within 24 hours (day -1) of the first dose of study drug in Cycle 1. For Cycle 2+, pregnancy testing to be performed on day 1 of each cycle prior to dosing of study drug. Subsequent testing at Cycle 2+ and at the end of study visit can be either urine or serum. Any positive urine pregnancy test must be confirmed with a serum test. Post-menopausal females: defined as 12 months with no menses prior to screening and a serum FSH >40 IU/L at screening only.

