12.3.11.1. Definition of Childbearing Potential: Female Subjects

A female subject is considered of childbearing potential if she:

- Is anatomically and physiologically capable of becoming pregnant, and
- Will be or could possibly be sexually active with a male while undergoing study treatment

A female subject is considered to be of non-childbearing potential (ie, physiologically incapable of becoming pregnant) if she:

- Is naturally postmenopausal (at least 12 months consecutive amenorrheic [amenorrhea following cancer therapy does not rule out childbearing potential] and without other known or suspected cause)

- Is surgically sterilized (ie, total hysterectomy and/or bilateral oophorectomy) with surgery completed at least 1 month before the first dose of study drug
- Has a documented congenital or acquired disorder that is incompatible with pregnancy

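### Section 12.3.10 and footnote i of Tables 3 and 4 define postmenopausal more loosely than inclusion criterion 12, so a site could wrongly skip later pregnancy tests in a woman with therapy-related amenorrhea (minor)

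*Protocol*

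**What the plan says.** Criterion 12, in the Synopsis and in Protocol 8.1, sets a default: "All females will be considered to be of childbearing potential unless they are naturally postmenopausal" or surgically sterilized. Natural menopause is then qualified as "at least 12 months consecutively amenorrhoeic [amenorrhea following cancer therapy does not rule out childbearing potential] and without other known or suspected cause". Section 12.3.11.1, which defines childbearing potential for female subjects, repeats that "amenorrhea following cancer therapy does not rule out childbearing potential" and also requires that there be no other cause. Neither text mentions FSH.

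Section 12.3.10 sets out the pregnancy tests for FCBP: serum at screening and within 24 hours of first dose, then later tests in urine or serum. On timing it says: "For Cycle 2+, pregnancy testing to be performed on day 1 of each cycle prior to dosing of study drug". It also provides for a test at the end-of-study visit. It closes with a statement that postmenopausal females are "defined as 12 months with no menses prior to screening and a serum FSH >40 IU/L at screening only". Footnote i of Table 3 carries the same sentence ("defined as 12 months with no menses prior to screening and a serum follicle-stimulating hormone (FSH) >40 IU/L at screening only"), as does footnote i of Table 4 ("Postmenopausal females: defined as 12 months with no menses prior to screening and a serum follicle-stimulating hormone (FSH) >40 IU/L at screening only").

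**The concern.** The two definitions classify the same woman differently, and she is foreseeable here. Criterion 5 admits solid tumors that have progressed after treatment and hematologic malignancies after at least two systemic lines, so amenorrhea caused by earlier treatment will occur in this population. The qualifier in criterion 12 is aimed at exactly this case, but it is missing where the tests are scheduled.

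What is at stake is subject safety, not the analysis. Section 12.3.11 says tazemetostat may cause fetal harm, and 12.6 stops study drug at once in a subject who becomes pregnant. The tests from Cycle 2 on are the scheduled means of finding an unsuspected pregnancy.

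**Working it through.** The plan states no figure to reproduce. The check is a comparison of texts, followed by a count of the tests exposed.

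**Step 1: the definitions side by side.**

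| Condition | Criterion 12 and 12.3.11.1 | 12.3.10 and footnote i (Tables 3, 4) |
|---|---|---|
| 12 months without menses | Required | Required |
| Amenorrhea after cancer therapy | Does not rule out childbearing potential | Not mentioned |
| No other known or suspected cause | Required | Not mentioned |
| FSH >40 IU/L | Not mentioned | Required, at screening |

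**Step 2: apply them to one woman.** Take 12 months of amenorrhea following chemotherapy, with FSH above 40 IU/L. Under criterion 12 and 12.3.11.1 she is not naturally postmenopausal, so she is FCBP. Under 12.3.10 and footnote i she meets every stated condition for postmenopausal. The definitions also differ in the other direction: a naturally amenorrheic woman with FSH of 40 or less is not FCBP under criterion 12, yet is not postmenopausal under 12.3.10. That mismatch could only lead to extra tests.

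**Step 3: which tests rest on which text.** Criterion 12 itself requires the negative serum tests at screening and within 24 hours of first dose, and Protocol 7.1 adds: "Prior to dosing on day 1 of Cycle 1, subject eligibility will be reconfirmed". The two entry tests are therefore secured. Contraception comes from criterion 13 and 12.3.11.3.1, not from footnote i. Only the Cycle 2+ and end-of-study tests depend solely on 12.3.10, footnote i and the schedule rows.

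**Step 4: count the exposed tests.** Let k be the number of cycles started from Cycle 2 on. Tests exposed per affected woman = k (day 1 of each cycle) + 1 (end of study) = k + 1.

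- k = 0: 1 test
- k = 1: 2 tests
- k = 9: 10 tests

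Here k = 9 is illustrative, taken from the rollover threshold of 9 cycles in 7.1. A subject who rolls over without an end-of-study visit has k tests exposed, which is 9 at k = 9.

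**Step 5: intervals, assuming full 28-day cycles and no visit window used.** Tested as FCBP, her longest on-treatment interval is 40 days in Part 1 (day -1 to day 40, with no day 0). In Part 2 it is 28 days (27 days from day -1 to day 27, then 28 per cycle). If the later tests were all omitted, the time from the day -1 test to last dose for k of 1 or more would be:

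- Part 1: 39 + 28k = 67 days at k = 1, 291 at k = 9
- Part 2: 26 + 28k = 54 days at k = 1, 278 at k = 9

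**The case against.** The best answer is that pregnancy testing depends on FCBP status, not on the postmenopausal sentence. Section 12.3.10 and both footnotes address all FCBP, and both visible definitions of that term keep this woman within it. The FSH sentence names no exemption, and its limitation to screening suggests that it describes a screening check. A site that had tested her at entry and applied contraception would have to change its classification of her to stop testing at Cycle 2.

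Most of this stands. A reader might infer that the protocol exempts such women from later testing, or that nothing in it indicates which definition governs. The documents support neither: 12.3.11.1 is titled as the definition, comes shortly after 12.3.10, and agrees with criterion 12. The day counts above are also the ordinary schedule multiplied by an assumed k, not a measured effect.

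What the objection does not remove is that 12.3.10 and the footnotes present their sentence as a definition, that it contradicts criterion 12, and that it stands beside the only instructions for the later tests. With about 24 centers planned, staff working from the schedule row should not have to resolve that themselves.

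**Conclusion.** The point holds as an inconsistency in a safety rule, at minor weight. The definition in 12.3.10 and footnote i is wrong as written for women with amenorrhea after cancer therapy or from another cause. Properly read, the protocol still tests them. The exposure is that a site may misread it and omit up to k + 1 later tests per affected woman.

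Neither the number of such women nor the likelihood of the misreading can be derived from the documents. It would go too far to say that any woman will go 291 or 278 days untested: that requires the misreading, nine further full cycles and omission of every later test. Entry tests, contraception duties, PK endpoints and sample size are unaffected. The conclusion covers the text available; the laboratory list in Appendix 2 was not part of it.

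**What to change.** In 12.3.10 and footnote i of Tables 3 and 4, replace the postmenopausal definition with a reference to criterion 12 and 12.3.11.1, carrying over the cancer-therapy and no-other-cause qualifiers. State there that FSH above 40 IU/L at screening is only an added confirmation of natural menopause and never exempts a woman who is FCBP under criterion 12.

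The same amendment could tidy three editorial mismatches in 12.3.11.1:

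- The sterilization interval is 1 month, against 28 days in criterion 12.
- It exempts women with a disorder incompatible with pregnancy, which criterion 12 does not list.
- Its sexual-activity condition sits awkwardly with criterion 13 and 12.3.11.3.1, which treat abstinent women as FCBP.

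The cost is one sentence in three places, plus any tidying of 12.3.11.1. FSH is already a screening item, so the only added burden is a few urine or serum pregnancy tests at sites that would otherwise have skipped them.
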